7.6.5 Handling of Missing Data

Data will be handled on an observed case basis with no imputation.

7.6.6 Safety Endpoints

Summaries will be presented to determine long-term safety in place of conducting statistical testing.

7.6.6.1 IGA Summary

The IGA will be summarized across the study duration in order to evaluate safety as it pertains to the underlying condition of papulopustular rosacea.

7.6.7 Demographic and Baseline Characteristics

Continuous demographic and baseline parameters will be summarized by the number of non-missing observations, mean, standard deviation, median, minimum, and maximum. Categorical parameters will be summarized by frequencies and percentages.

CONFIDENTIAL

Version Date: 07 March 2017

7.6.8 Subject Disposition

Study completion status and reasons for discontinuation will be summarized by frequencies and percentages.

7.6.9 Study Product Exposure

The number of days of exposure will be summarized by the number of non-missing observations, mean, standard deviation, median, minimum, and maximum.

7.6.10 Safety Summaries

Adverse events will be categorized by SOC and Preferred Term from the current version of MedDRA. The focus of the adverse event summaries will be on treatment-emergent adverse events. Treatment-emergent adverse events will be summarized overall, by severity, and by relationship to study product.

Changes or shifts in safety laboratory data and vital signs will be summarized at all time-points when available. Summaries will include means, standard deviations, median, minimum and maximum values for continuous data, or frequency and percent for categorical data. Additionally, shift tables will be provided for abnormal safety labs.

8 ETHICS AND GENERAL STUDY CONDUCT CONSIDERATIONS

8.1 ETHICAL CONDUCT OF THE STUDY

This study will be conducted in accordance with the FDA and ICH guidelines on current GCP, and following the ethical principles originating from Declaration of Helsinki. Additionally, the study will be conducted in accordance with any applicable laws or regulations of the country in which the clinical research is conducted.

8.2 CHANGES IN STUDY CONDUCT/STATISTICAL ANALYSES/AMENDMENTS

No change in the conduct of the study should be instituted without written approval from the CRO/Sponsor, and the IRB/IEC. Substantial Amendments to the protocol require written approval from the Sponsor, Institutional Review Board, ethics committee and the regulatory authority, as applicable.

8.3 INSTITUTIONAL REVIEW BOARD (IRB) /INDEPENDENT ETHICS COMMITTEE (IEC)

This study protocol, all appropriate amendments, all advertising, and written materials given to the subjects will be reviewed and approved by an Institutional Review Board/Independent Ethics Committee, prior to use.

CONFIDENTIAL

Version Date: 07 March 2017

8.4 SUBJECT INFORMATION AND CONSENT

The study personnel will inform all subjects in this study, in accordance with GCPs, about the study. The study personnel will review the informed consent form (ICF) with each subject and give the subject an opportunity to read the consent and have all questions answered before proceeding. A current written consent form, approved by an IRB/IEC, is to be supplied by the Investigator and willingly signed by each subject prior to initiating any study procedures, including instructing the subject to discontinue the use of medications requiring wash-out. The Investigator is responsible for maintaining each subject's consent form in the study file and providing each subject with a copy of the signed form(s).

8.5 PROTOCOL ADHERENCE

The Investigator must read the protocol thoroughly and must follow the instructions exactly. Any change should be agreed upon by prior discussion between the CRO/Sponsor and the Investigator, with appropriate written protocol amendments made prior to implementation of the agreed-upon changes. Any amendment containing major modifications (particularly if it may involve an increased risk to the subjects) will be approved by the IRB/IEC before it may be implemented.

8.6 CONTRACTUAL REQUIREMENTS

A contractual agreement will be signed between the Sponsor/CRO and the Investigator/clinical site. This document will contain complementary information, i.e. financial agreement, confidentiality, study schedule, and publication of study results.

8.6.1 Publication policy

All data generated from this study are the property of the Cutanea Life Sciences, Inc. Publication of data will be done in accordance with the contractual agreement between the Sponsor/CRO and Investigator/clinical site.

8.7 RECORD KEEPING

8.7.1 Data Collection

The Investigator must maintain detailed records on all study subjects. Data for this study will be recorded in the subject's chart and entered into eCRFs through the electronic data capture (eDC) system provided by the Sponsor's designated data management group. Applicable data from the subject's chart should be recorded in the eCRFs completely, promptly, and taking time to correct any mistakes as prompted by the eCRF system. Upon study completion or at any other time specified by the CRO/Sponsor, a monitor will review the appropriate eCRF data.

CONFIDENTIAL

Version Date: 07 March 2017

Completed eCRFs should be ready for review by the CRO/Sponsor's Monitor, within one (1) week of each study visit for a given subject.

8.7.2 Data Corrections

Corrections of data entered into the eCRF must be made in the system for electronic case report forms, as appropriate.

- The CRO/Sponsor's Monitor will review the eCRFs, evaluate them for completeness and accuracy, and ensure that all appropriate information is entered.
- No changes will be made to the data on the eCRF pages after the data are determined to be final by the CRO/Sponsor's Monitor and data management group. Queries and comments may still be generated and answered on eCRFs as outlined in the eDC system.

8.7.3 Source Documentation

Investigators must keep accurate separate records (other than the eCRF) of all subjects' visits, which include all pertinent study-related information including the original signed/dated informed consent and drug accountability records. As a minimum, a statement should be made in the subject's record indicating that the subjects have been enrolled in Protocol CLS001-CO-PR-006 and that they signed an informed consent form. Any adverse events must be thoroughly documented. Results of any diagnostic tests conducted during the study should also be included in the source documentation. Telephone conversations with the subjects and/or the CRO/Sponsor concerning the study must also be recorded.

8.7.4 Monitoring/Auditing

Representatives of the CRO/Sponsor, following GCP guidelines, will monitor the conduct of the study. In addition, inspections or on-site audits may be carried out by the FDA, local regulatory authority or by the CRO/Sponsor's independent Quality Assurance Department. The Investigator will allow the CRO/Sponsor's representatives and any regulatory agency to examine all study records, eCRFs, corresponding subject medical records, clinical drug dispensing records, drug storage area, and any other documents considered source documentation.

8.7.5 Archives

Records must be retained in accordance with the current ICH Guidelines on GCP. All essential study documents including records of subjects, source documents, eCRFs and study drug inventory must be kept on file.

CONFIDENTIAL

Version Date: 07 March 2017

Essential documents should be retained until at least 2 years after the last approval of a marketing application in the an ICH region and until there are no pending or contemplated marketing applications in an ICH region, or until at least 2 years have elapsed since the formal discontinuation of clinical development of the investigational products. However, essential documents may be retained for a longer period if required by the applicable regulatory requirements or by agreement with the Sponsor. The Sponsor is responsible for informing the Investigator when these documents need no longer be retained.

The Investigator will not dispose of any records relevant to this study without written permission from the Sponsor, and will provide the Sponsor the opportunity to collect such records. The Investigator shall take responsibility for maintaining adequate and accurate hard copy source documents of all observations and data generated during the study. Such documentation is subject to inspection by the Sponsor, its representatives, and regulatory authorities.

If the Principal Investigator retires, relocates, or for other reasons withdraws from the responsibility of keeping the study records, custody must be transferred to a person who will accept the responsibility. The CRO/Sponsor must be notified in writing of the name and address of the new custodian.

[REDACTED]

[REDACTED]

[REDACTED]

[REDACTED]

[REDACTED]

[REDACTED]

11 APPENDICES

Appendix A**Instructions On Application Of Study Drug**

You should apply study drug once daily, preferably in the morning.

Before applying the study drug:

1. Wash your hands and face before applying study medication.
2. For the first dose, the study staff will review treatment application with you before you apply the study drug. The amount of product that you will apply each day should be a sufficient amount to cover your face with a thin layer of gel.

Application of the study gel:

1. Remove the cap from the study medication tube and squeeze a small line of product from the crease of your last knuckle to the tip of your finger (see picture below). The line should be approximately the width of the tip of the tube.

2. Next, apply the product in a thin layer by gently dabbing and blending it evenly over your entire face, including cheeks, chin, forehead and nose, avoiding the corners of the eyes, mouth and inside your nose.
3. If additional product is needed to cover your face, then squeeze very small amounts of product from the tube and blend it evenly on the untreated areas of your face until your entire face has a thin layer of product applied to it. If you notice dried or flaking product on your face, you may be applying too much product.
4. Return the cap to the study medication tube and store the tube of study medication at room temperature.
5. Record your treatment application on your diary
6. Keep clothing off of the treated areas until the gel is dry.

You must not apply more than the recommended dose at any application.

- Showering/bathing (when you shower or bathe, use a non-medicated soap or soapless cleanser and wait at least 15 minutes prior to applying study drug).
- Wait until the gel is dry before applying makeup.
- Excessive exposure to the sun and tanning booths/beds should be avoided. Wait until the gel has dried before applying sun screen to your face.
- No new lotions, gels, powders, moisturizers, etc. and no topical medications are to be used on the skin in the treatment areas.

Remember to bring your tubes and diary back to the clinic at EVERY visit. Please call the clinic immediately if you have lost your tubes.

Clinic Phone number: _____ Your next appointment is: _____

CONFIDENTIAL

Version Date: 07 March 2017

Appendix B

Fitzpatrick skin type classification:

- I: Always burn, never tan
- II: Usually burn, tan less than average (with difficulty)
- III: Sometimes mild burn, tan about average
- IV: Rarely burn, tan more than average (with ease)
- V: Rarely burns, tans profusely
- VI: Never burns, tans profusely

1. Fitzpatrick TB. The validity and practicality of sun-reactive skin types I through VI. Arch.Dermatol. 1988; 124: 869-871.
2. Sachdeva S. Fitzpatrick skin typing: Applications in dermatology. Indian J Dermatol Venereol Leprol 2009;75:93-6

## 1.0 Introduction

Rosacea is a chronic dermatologic disorder that primarily affects the facial skin. An estimated 16 million Americans have rosacea. The clinical signs and symptoms of rosacea are: facial flushing, telangiectasia, facial erythema, central facial inflammatory papules and pustules, hypertrophy of the sebaceous glands of the nose and ocular changes. Rosacea has been classified into four different subtypes; Subtype 1: erythematotelangiectatic, Subtype 2: papulopustular, Subtype 3: phymatous and Subtype 4: ocular. Each subtype has severity grades ranging from mild to severe.

Currently, there is no cure for rosacea and the etiology is poorly understood. Many theories regarding the cause of rosacea have been highlighted in the literature. The pathology of rosacea may be multifactorial: abnormal vascular and immune system responses; hair follicle mite *Demodex folliculorum*; bacteria such as *Helicobacter pylori*; prolonged steroid use and other aggravating trigger factors like sun and stress. Gallo and his colleagues found an abnormally high level of the naturally occurring antimicrobial peptide cathelicidins upon histopathological staining in the skin of patients with rosacea.

Cutanea Life Sciences is developing omiganan topical gel for the treatment of papulopustular rosacea. The exact cause of rosacea is unknown and may be in due in part to an inflammatory process. Recent research has shown that cationic peptides such as omiganan may have anti-inflammatory properties and may play a role in inhibiting the inflammatory response. Omiganan may also prevent the inflammatory cascade that is theorized to lead to the signs and symptoms of rosacea. A possible anti-inflammatory activity of omiganan is suggested by the observation of a reduction in inflammatory acne lesion counts with omiganan in two Phase 2 clinical trials. However, the exact mechanism of action is undetermined.

Two previous clinical studies of omiganan in rosacea were conducted. CLS001-R-001 was a double-blind, multicenter, randomized, vehicle-controlled, parallel group study in 240 adult subjects with subtype 2 papulopustular rosacea. Eligible subjects were randomized to 5 treatment groups in a 2:2:2:1:1 ratio. The treatment arms were Omiganan topical gel at 1% QD, 2.5% QD, 2.5% BID, and Vehicle QD and Vehicle BID. Subjects were treated for 9 weeks. In the MITT analysis, all efficacy variables improved compared with Baseline in all treatment groups. The reductions from Baseline tended to be greatest in the omiganan 2.5% QD group; however, there were no statistically significant differences between the active treatment groups and the combined vehicle group for any efficacy variable at the Week 9/end of treatment endpoint for the MITT population.

Based upon the results of the first Phase 2 study in rosacea, Cutanea determined that the dose-response relationship of omiganan warranted further exploration. An additional Phase 2B study CLS001-CO-PR-001 investigated the safety and efficacy of once-daily omiganan 1%, 1.75% and 2.5% compared to vehicle gel. Again this was a double-blind, multicenter, randomized, vehicle-controlled, parallel group study in 240 adult subjects with subtype 2 papulopustular rosacea. Subjects were randomized into 4 test groups at a 1:1:1:1 ratio and observed over the course of 12 weeks. In addition to the primary analysis of the change from baseline in inflammatory lesion counts for the ITT population, several strata based on baseline lesion counts were also evaluated

in post hoc analyses. The efficacy signal was improved with increasing baseline lesion count, and was best for the [REDACTED] omiganan treatment group.

## **2.0 Study Design**

This study will be conducted in accordance with FDA guidelines on current Good Clinical Practice (GCP) and the ethical principles that have their origins in the Declaration of Helsinki.

The study will be conducted as an open-label, multicenter study at approximately 30 sites and involving 300 subjects with subtype 2, papulopustular rosacea. After giving informed consent, each subject will be screened for study eligibility according to specific inclusion/exclusion criteria. Eligible subjects will be enrolled to evaluate the long-term safety of omiganan [REDACTED] topical gel.

Omiganan gel will be topically applied once daily to the entire facial area; cheeks, chin, forehead and nose, avoiding contact with the eyes, mouth, and other mucous membranes.

Following baseline testing and evaluation for acceptance into the study, the subjects will be supervised during the first test drug application on Day 1 to ensure that the study treatment is applied correctly. Thereafter, each subject will apply the study treatment at home (unsupervised) once daily for up to 12 months. Once 100 subjects have completed a year of treatment, the remaining subjects will discontinue treatment after a minimum of six months. Other concurrent therapies will be recorded throughout the study. A bland unmedicated soap or soapless cleanser should be used for the purposes of washing the subject's face.

Safety assessments will be done on all of the designated study visit days.

### **3.0 Study Objectives**

The primary objective of this study is to evaluate the long-term safety of Omiganan [REDACTED] topical gel applied once daily to the face of subjects with severe papulopustular rosacea.

### **4.0 Statistical Methodology**

No statistical testing will be performed. Continuous parameters will be summarized by N (number of non-missing observations), mean, standard deviation, median, minimum, and maximum. Categorical parameters will be summarized by count and percent.

#### **4.1 Sample Size**

The sample size for this study is based upon ICH E1.

#### **4.2 Study Populations**

The “All-treated” analysis population will consist of all subjects receiving at least one application of study medication. All safety analyses will be performed on the all-treated population.

#### **4.3 Statistical Analysis**

##### **4.3.1 Subject Accounting, Demographic, and Baseline Characteristics**

Demographic, baseline characteristics (including physical examinations, and subject reported signs and symptoms of rosacea), and prior and concomitant medications will be summarized. Study completion status and reasons for discontinuation will also be displayed by treatment.

Medical history and previous rosacea therapies taken within the last five years will only be presented in the listings.

##### **4.3.2 Safety Summaries**

The IGA will be summarized across the study duration in order to evaluate safety as it pertains to the underlying condition of papulopustular rosacea.

Adverse events will be categorized by SOC and Preferred Term from the current version of MedDRA. The focus of the adverse event summaries will be on treatment-emergent adverse events. Treatment-emergent adverse events will be summarized overall, by severity, and by relationship to study product.

Changes in safety laboratory data, vital signs, and physical exam will be summarized at all time-points when available. Summaries will include means, standard deviations, median, minimum and maximum values for continuous data, or frequency and percent for categorical data. Additionally, shift tables will be provided for abnormal safety labs.

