1 SYNOPSIS

Title of Study: A Phase 3 Open-Label Extension Study to Evaluate the Long-Term Safety of Omiganan Topical Gel in Subjects with Rosacea
	

Study Period (Planned): Start –First subject enrolled: [REDACTED] End – Last subject last visit: [REDACTED]
	
Phase of Development: Phase 3

Objectives: To evaluate the long-term safety of omiganan topical gel applied once daily to the face of subjects with papulopustular rosacea
	

Methodology: Open-label, multi-center, long-term safety study
	

Number of Subjects (planned): Up to 300 enrolled, to achieve up to 300 evaluable at 6 months and up to 100 at 12 months
	

Number of Sites: Approximately 35 sites in the United States, Canada, France, Netherlands, United Kingdom, Sweden, Australia and New Zealand.
	

Diagnosis and Main Criteria for Inclusion:
 
 • Male or non-pregnant female subjects at least 18 years of age with severe papulopustular rosacea (IGA score of 4) 	

Investigational Product: Omiganan topical gel Comparator Product: None
 
Dose: Apply once daily (Preferably in the morning), as a thin film, to the entire face (Approximately 0.4 grams) Mode of Administration: Topical application to the entire face avoiding contact with the mouth, eyes and inside the nose Duration of Treatment: Up to 12 months (52 Weeks ± 14 Days)
	

Criteria for Evaluation:
 
Safety: Adverse events (AE) throughout the study at Month 1, 3, 6, 9, 12. Physical exam, vital signs, immunogenicity and safety labs will be collected at select time-points.
 
Statistical Methods: Safety: Adverse events will be categorized by SOC and Preferred Term from the current version of MedDRA. Changes or shifts in safety laboratory data and vital signs be summarized at all time-points when available. Summaries will include means, standard deviations, median, minimum and maximum values for continuous data, or frequency and percent for categorical data. Additionally, shift tables will be provided for abnormal safety labs.
	

CONFIDENTIAL

Version Date: 07 March 2017

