5.2 RATIONALE

To date, the safety of omiganan pentahydrochloride topical gel [REDACTED] has been evaluated in subjects exposed to treatment for 12 weeks. This study is being conducted to meet recommendations of ICH-E1a and FDA guidance that 300 subjects be exposed for 6 months and 100 subjects exposed for one year to evaluate the long term safety of drugs intended for long-term treatment (chronic or repeated intermittent use for longer than 6 months). This study is designed contribute up to 300 of the required 300 subjects exposed for 6 months and up to 100 subjects exposed for one year. The Phase 3 Pivotal study (CLS001-CO-PR-004) has an open label extension phase which is designed to also contribute subjects required to fulfill 300 subjects exposed to study drug for 6 months and 100 subjects exposed for one year. The enrollment and completion of the study participants will be monitored via the electronic data collection system to determine when sufficient numbers of subjects have completed the studies to meet the long term safety exposure requirements.

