7 INVESTIGATIONAL PLAN

7.1 OVERALL STUDY DESIGN

This study will be conducted in accordance with the FDA and ICH guidelines on current GCP, and following the ethical principles originating from the Declaration of Helsinki. Additionally, the study will be conducted in accordance with any applicable laws or regulations of the country in which the clinical research is conducted.

The study will be conducted as an open-label, multicenter study at approximately 35 sites in the United States, Canada, , France, Netherlands, United Kingdom, Sweden, Australia and New Zealand and involving approximately 300 subjects with severe papulopustular rosacea. After giving informed consent, each subject will be screened for study eligibility according to specific inclusion/exclusion criteria. Eligible subjects will be enrolled to evaluate the long-term safety of omiganan topical gel. Omiganan gel will be topically applied once daily to the entire facial area; cheeks, chin, forehead and nose, avoiding contact with the eyes, mouth, and inside the nose.

Following baseline testing and evaluation for acceptance into the study, eligible subjects will be supervised during the first test drug application on Day 1 to ensure that the study treatment is applied correctly. Thereafter, each subject will apply the study treatment at home (unsupervised) once daily for up to 12 months. Once 100 subjects have completed

CONFIDENTIAL

Version Date: 07 March 2017

one year and 300 subjects have completed 6 months of treatment with omiganan topical gel (in the CLS001-CO-PR -004 and -006 studies combined), the remaining subjects in this study will discontinue treatment and will have their final study visit performed and no additional subjects will be recruited.

Other concurrent therapies will be recorded throughout the study. A bland non-medicated soap or soap less cleanser should be used throughout the study for the purposes of washing the subject's face.

Safety assessments will be done on all of the designated study visit days. The end of the study will be the date that the last study subject completes the last visit for the study.

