7.6.4 Analysis Population

The “All-treated” analysis population will consist of all subjects receiving at least one application of study medication. All analyses will be performed on the all-treated population.

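### No adverse event summary by time is planned although follow-up is unequal by design, so the planned table cannot show late onset or risk by Months 6 and 12

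*SAP*

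**What the plan says.** **Adverse events.** SAP 4.3.2 and protocol 7.6.10 classify events by MedDRA class and term and then say: "Treatment-emergent adverse events will be summarized overall, by severity, and by relationship to study product". The sentence names no statistic. SAP 4.0 supplies the general rule: "Categorical parameters will be summarized by count and percent". SAP 4.2 supplies the denominator: "All safety analyses will be performed on the all-treated population". Protocol 7.6.4 agrees: "All analyses will be performed on the all-treated population".

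**Time wording elsewhere.** In SAP 4.3.2 the reference to time-points covers laboratory data, vital signs and physical exam, and the reference to study duration covers the IGA. The protocol synopsis lists visit months for adverse events under evaluation criteria, not under statistical methods.

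**Follow-up.** The protocol synopsis plans "Up to 300 enrolled, to achieve up to 300 evaluable at 6 months and up to 100 at 12 months". Under protocol 7.1, once the one-year and six-month targets are met in studies -004 and -006 combined, "the remaining subjects in this study will discontinue treatment and will have their final study visit performed". SAP 2.0 says instead that once 100 subjects have a year of treatment, "the remaining subjects will discontinue treatment after a minimum of six months".

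**Other planned tables.** Days of exposure are summarized on their own (SAP 4.3.4). Completion status and reasons for discontinuation are given as counts and percentages (SAP 4.3.3, protocol 7.6.8).

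**The concern.** Long-term safety is the only objective (protocol 6). By protocol 5.2, the gel's safety "has been evaluated in subjects exposed to treatment for 12 weeks". What this study can add is mainly what happens after that: whether events begin late, and how many subjects have had one by Month 6 and by Month 12.

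A single percent over mixed follow-up answers neither question. An event in Week 2 and an event in Month 10 count alike, and the denominator includes subjects who were never observed in the second half of the year. A reader who takes the percent as the risk over a year of use would understate that risk for any event that keeps occurring after the early stop.

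**Working it through.** **The plan's own figure.** There is none to reproduce. The sample size follows guideline exposure counts (protocol 7.6.2, SAP 4.1), and no event rate, precision or dropout is stated.

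**Inputs.**
- From the documents: up to 300 subjects, up to 100 of them to Month 12, a maximum of 12 months, and early stopping of the rest.
- Assumed: a true 12-month risk R = 10%, the split of follow-up, the hazard shape, and no other dropout.

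**Crude percent.** With n subjects followed to Month 12 and 300 − n stopped at month t:

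crude = [n × R + (300 − n) × F(t)] / 300, where F(t) is the risk by month t.

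*Constant hazard.* h = −ln(1 − R)/12 per month, so F(6) = 1 − √0.9 = 0.0513. With n = 100:
(100 × 0.10 + 200 × 0.0513)/300 = 20.26/300 = **6.75%**.

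*Onset only after Month 6.* F(6) = 0, so (100 × 0.10 + 0)/300 = **3.33%**.

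*Onset only before Month 6.* F(6) = R, so (100 × 0.10 + 200 × 0.10)/300 = **10%**, with no shortfall.

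**Other splits, same formula, the rest stopped at Month 6:**

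| To Month 12 / to Month 6 | Constant hazard | Onset only after Month 6 | Onset only before Month 6 |
|---|---|---|---|
| 50 / 250 | 5.94% | 1.67% | 10% |
| 100 / 200 | 6.75% | 3.33% | 10% |
| 200 / 100 | 8.38% | 6.67% | 10% |
| 300 / 0 | 10% | 10% | 10% |

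**Other stopping times** (n = 100, constant hazard). Stopping the 200 at Month 9 gives 8.40%. Spreading their stops evenly over Months 6 to 12 gives 8.39%. Stopping them at Month 3 gives 5.07%; protocol 7.1 does not exclude this for an individual subject, while SAP 2.0 does apart from dropout.

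**Does a time-based estimate recover the risk?** Take the 100/200 split and expected counts. By Month 6, 300 × 0.0513 = 15.4 have had an event, so survival is 0.9487. After the 200 stop, 94.87 remain at risk and 4.87 more have an event: 4.87/94.87 = 0.0513. Kaplan-Meier at Month 12 = 1 − 0.9487 × (1 − 0.0513) = 10%. With late onset only, it is 10 of 100 = 10%. Both results need censoring unrelated to event risk.

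**Precision.** An observed 6 of 100 has an exact 95% CI of 2.2% to 12.6%. If only 50 are at risk after Month 6, with late onset and R = 10%, the estimate is Binomial(50, 0.1)/50. P(X = 0) = 0.9^50 = 0.005 is below 0.025 and P(X ≤ 9) = 0.9755, so the central 95% runs from 1/50 = 2% to 9/50 = 18%.

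**The case against.** The strongest reply is that the plan misses no stated target. The study is single-arm and descriptive, without testing (protocol 7.6.1, SAP 4.0), and is sized to exposure counts. A reader might infer that the adverse event table is biased, or that the sponsor presents it as a 12-month risk. The documents support neither reading. The percent is a correct proportion over the follow-up that occurred, no section labels it as risk over a year, and even its form is inferred from the general rules rather than stated in the adverse event sentence.

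It can also be said that other tables fill the gap. They do so in part. The exposure summary shows how unequal follow-up was, and disposition shows who completed, with termination by the sponsor as a separate reason (protocol 7.2.3). But neither is linked to adverse events, and completion is not defined for subjects stopped under protocol 7.1. For vital signs, protocol 7.4.3 combines Month 12 with early termination, so that visit count is not a clean Month 12 risk set.

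Finally, the -004 extension also supplies long-term exposure (protocol 5.2, 7.1), so this study need not carry the question alone. That stands, and it has a second consequence: fewer than 100 subjects here may reach Month 12. Whether a pooled time-based analysis is planned elsewhere cannot be seen from these documents.

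**Conclusion.** The gap is real and worth fixing. As written, the plan does not show when adverse events begin or the risk by Months 6 and 12, in a study whose sole objective is long-term safety. The absence of timing holds whatever the follow-up mix turns out to be.

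The numerical shortfall is conditional. In the example it is 6.75% or 3.33% against a true 10%, but the follow-up split, the hazard shape and the 10% are all assumptions, so these figures are illustrations and not bounds. There is no shortfall if events occur early or if all subjects reach Month 12. A reader might infer that long-term risk will be understated in the report; that does not follow, because the size depends on accrual and event timing that the documents do not fix.

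Protocol 7.1 and SAP 2.0 also differ on whether a stopped subject has a six-month minimum, and on whether the trigger counts both studies. The passages must be reconciled, because they determine the follow-up mix.

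**What to change.** In SAP 4.3.2 and protocol 7.6.10, keep the crude table and add the following for any treatment-emergent event, related events, serious events and events leading to discontinuation:

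- **Kaplan-Meier cumulative incidence of first event at Months 6 and 12**, with numbers at risk and 95% CIs. State the end of time at risk used for censoring. Define the landmark day so that the 14-day visit window (protocol 7.3.2) does not remove completers from the risk set. For example, if Week 52 is counted as Day 364, a visit 14 days early falls on Day 350.
- **Events by onset interval per person-time within the interval**, stating whether first events or all events are counted and matching the person-time to that choice.

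Add a sentence that early withdrawal may be informative, since adverse events, physician decision and non-compliance are listed reasons (protocol 7.2.3). Define completion for subjects stopped under protocol 7.1, and reconcile that section with SAP 2.0.

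**Cost.** Wording and a few tables, with no new visits, data or subjects: onset date (protocol 7.4.7.1) and last application date (protocol 7.5.1) are already collected. The additions remain descriptive. Month 12 estimates will be imprecise, as the intervals above show, and the report should say so.
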